**Data Analysis and Monitoring:**

**Subject disposition:** The frequency and reason for subject withdrawal will be summarized.

**Data Analysis and reporting:** The PI and sub-investigators will be responsible for performing all analyses, creating the output for the analyses and disseminating results to the study team. The Principal Investigator and the rest of the study team will then review the results. The Principal Investigator will be responsible for drafting and preparing a final report of the study.

**Data Storage and Confidentiality:** The data will be stored on password protected computers in the UCSF Pediatric Dental Clinic in a password protected room. Only investigative personnel will have access. The data will be available for inspection by regulatory monitors and FDA.

**Risk-Benefit Assessment**

**Risk Category:** Minimal Risk.

**Potential Risk:** Hypersensitivity to silver or fluoride, changes to intraoral tissues: erythema, gingival inflammation, or soft tissue changes. Advantage Arrest has been

used extensively since clearance as a medical device in 2014 and the Sponsor knows of no adverse effects. The same agent is approved in Canada and Japan and there have no harms reported. There may be bruising at the site of the blood collection.

**Protection Against Risks:** The study will be carried out at UCSF Benioff Children's Hospital in the University of California, San Francisco in Pediatric Dental Clinic and the Clinical and Translational Science Institute by licensed personnel under the Clinical and Translational Science Institute.

**Potential Benefits:** The Advantage Arrest will help slow or arrest their existing carious lesion/s and aid in the prevention of new lesions.

**Alternatives to Participation:** The alternative is to decline participation.

### **Subject Identification, Recruitment and Consent/Accent**

**Method of Subject Identification and Recruitment:** Subjects will be recruited among patients at the University of California, San Francisco Pediatric Dental Clinic. Flyers will also be posted in at the University of California, San Francisco Pediatric Dental Clinic to notify potential subjects of the opportunity to participate. They will call or email [name] for more information or to schedule an appointment. Subjects who meet the study's criteria for entry will be recruited into the study by the PI and enrolled.

**Process of Consent:** Potential subjects will have the opportunity to ask questions and will be informed that participation is voluntary. They will have the opportunity to take the consent home to consider whether or not they want their child to take part in the study. They will be reminded that whether or not they decide to participate will not affect their care at University of California, San Francisco Pediatric Dental Clinic and they can ask questions about participation or discontinue participation at any time.

**Process of Assent:** Potential subjects will have the opportunity to ask questions and will be informed that participation is voluntary. All communication will be had at an age-appropriate level. They will have the opportunity to take the assent home to consider whether or not they want to take part in the study. They will be reminded that whether or not they decide to participate will not affect their care at University of California, San Francisco Pediatric Dental Clinic and they can ask questions about participation or discontinue participation at any time.

**Minimize Pressure to Participate:** Pressure to participate will be minimized by ensuring all subjects are aware that their decision to participate or not will have no consequences. They can say yes or no, and nothing will be different. Everyone will be just as happy with them.

**Parent/Subject Capacity:** Parents must have the capacity to give informed consent and subjects must have the capacity to give assent. Subjects must be English speaking and able to read and understand English.

**Parent/Subject Comprehension:** Potential parents and subjects will be asked to clarify their understanding of the objectives of the study. They will also be asked to clarify their understanding of the risks and benefits of participation.

**Documentation of Consent and Assent:** Once potential parents and subjects have had a chance to read the approved consent and assent forms, and had their questions answered following the consent/assent discussion, they will be asked to sign the forms. The study staff will sign the form and provide the participant a fully signed and dated copy. The original signed consent and assent forms will be stored in a locked cabinet at the University of California, San Francisco Pediatric Dental Clinic at Benioff Children's Hospital.

**Costs to the Subject:** The participants will not incur any costs associated with the study.

**Payment for Participation:** A \$100 volunteer compensation will be provided.

**Reimbursement for Participation:** Reimbursement will be provided to defray the costs of parking and transportation for study participation.

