In both studies, the dose and time to peak serum silver was comparable. Peak serum silver concentrations were higher in the Vasquez et al study which could be due to lack of rinsing post-application. In both studies, there was a 400-fold safety margin in the amount applied compared to the US EPA's lowest allowable effect level for silver exposure at 1g.

There are no published PK studies with children. The investigative team at the University of Washington developed a physiologically-based pharmacokinetic (PBPK) model to predict silver disposition in children, as there are data establishing the safety of fluoride exposure in children in both the anesthesia and dental literature. The predictive performance of the model was assessed by comparing the predicted PK profiles and parameters with the observed data from published rat and human data following intravenous or oral silver administration. The PBPK model was applied to the pediatric population by accounting for developmental physiological changes. From this model, the predicted silver concentrations were within 2-fold of observed blood and tissue silver concentrations in rats and within the 95% confidence interval of observed plasma silver concentrations in healthy human adults. For a given SDF dose, the simulated peak plasma silver concentrations were 5.2-, 4.3-, 2.7-, 1.3-fold higher in children aged 1-2

years, 2-4 years, 5-10 years and 12-17 years, respectively, compared to adults. The half-life of silver was comparable in all ages and plasma and tissue silver concentrations were predicted to return to baseline levels within 10 days after SDF application. Based on the predictions, younger children will have transiently higher silver plasma concentrations than adults, though smaller increases are expected if less SDF is applied.

**Assumptions for Proposed Study:** This is a topical agent where the active ingredients are applied to the teeth and eventually swallowed and may be absorbed through the GI tract or excreted. Minimal amounts are absorbed through the oral mucosa. Serum concentrations of silver and fluoride will be proportional to the dose of silver and fluoride administered topically to the teeth as part of Advantage Arrest.

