### **Criteria for Subject Selection**

**Number of subjects:** There will be up to 50 healthy children subjects enrolled in the study with the goal of at least 21 subjects to complete the study.

**Gender of subjects:** The subjects will be approximately half male and half female.

**Age of subjects:** Subjects will be 5-12 years of age.

**Racial and Ethnic Origin:** In a small study it is not possible to fully represent the racial/ethnic distribution of the region or US. The investigator will attempt to recruit a racial/ethnic diverse population.

**Inclusion criteria:** Subjects will be healthy. Healthy status will be determined by self-reported medical history evaluated by the attending clinician. Subjects will have at least one carious lesion.

**Exclusion criteria:** Subjects will be excluded if they have oral mucositis, any ulcerative lesions, or hypersensitivity to silver or fluoride. Subjects with a history of SDF treatment within 3 months will be excluded.

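### Applied literally, the English-reading rule is an unlisted, age-dependent eligibility restriction that could under-represent the youngest children in the 5-12 range

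*Combined protocol and SAP*

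**What the plan says.** Criteria for Subject Selection sets the age range: "Subjects will be 5-12 years of age". The inclusion criteria there are good health and a lesion ("Subjects will have at least one carious lesion"). Neither the inclusion nor the exclusion criteria mention language or reading.

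The language rule appears later, in the recruitment and consent section under Parent/Subject Capacity. That paragraph first separates two roles: "Parents must have the capacity to give informed consent and subjects must have the capacity to give assent". It then adds: "Subjects must be English speaking and able to read and understand English".

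Two nearby paragraphs bear on how the rule would work. Process of Assent promises: "All communication will be had at an age-appropriate level". Documentation of Consent and Assent places signature after reading by both parties: "Once potential parents and subjects have had a chance to read the approved consent and assent forms". The protocol text describes no route for a child who cannot yet read.

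The background gives the model predictions for silver: "For a given SDF dose, the simulated peak plasma silver concentrations were 5.2-, 4.3-, 2.7-, 1.3-fold higher in children aged 1-2" years, 2-4, 5-10 and 12-17 years respectively, relative to adults.

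**The concern.** A requirement that the child can read works as an eligibility criterion, and children are more likely to fail it the younger they are. Staff who follow the eligibility section would enrol a 5-year-old who does not read. Staff who follow the capacity paragraph literally would turn the same child away. The second course also sits badly with the promise to pitch assent at the child's level.

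The study is meant to add to the safety evidence in children, and the protocol's own model predicts higher peak silver at younger ages for a given dose. If the youngest eligible children are under-represented, the sample moves towards lower predicted peak exposure, which is the less cautious direction for a safety study. The ceiling of 50 enrolled protects the target of 21 completers but not the age mix, because replacements must pass the same reading rule.

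**Working it through.** **Who must read.** Three places bear on this.
- The sentence before the rule gives consent to parents and assent to subjects, so subjects there are the children.
- Documentation of Consent and Assent has parents and subjects each reading and signing, which fits that reading.
- Process of Consent points the other way: the potential subjects there are people deciding for their own child, so they are parents.

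The child is the more natural reading, but the text does not settle it.

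**The plan's own figure.** Blood sampling uses 3 children at each of 7 post-dose times: 3 × 7 = 21, which matches the stated target of completers.

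**Share of children lost.** Assumption: equal numbers at each single year of age from 5 to 12, that is 8 year groups. The documents give no reading rates, so only a range can be shown.
- All 5- and 6-year-olds read: 0/8 = 0%.
- No 5-year-old reads, all 6-year-olds do: 1/8 = 12.5%.
- No 5- or 6-year-old reads: 2/8 = 25%, or 21 × 0.25 = 5.25 of 21 children. About 21/0.75 = 28 age-eligible children would then be needed to yield 21.

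**Effect on predicted peak silver, using the stated bands.** The fold values are read as child:adult ratios at a given dose: 2.7 for ages 5-10 and 1.3 at age 12. Age 11 falls in no band, so its value x is allowed to run from 1.3 to 2.7.
- All ages: mean = (6 × 2.7 + x + 1.3)/8, which is 18.8/8 = 2.35 for x = 1.3 and 20.2/8 = 2.53 for x = 2.7.
- Without age 5: mean = (5 × 2.7 + x + 1.3)/7, which is 16.1/7 = 2.30 or 17.5/7 = 2.50. The fall is 2.1% or 1.0%.
- Without ages 5-6: mean = (4 × 2.7 + x + 1.3)/6, which is 13.4/6 = 2.23 or 14.8/6 = 2.47. The fall is 5.0% or 2.3%.
- If no child is lost, the fall is 0%. The highest ratio covered is 2.7 in every case.

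**Sensitivity: interpolating within the bands (assumption).** Take the logarithm of the ratio as linear between band midpoints 3, 7.5 and 14.5 years.
- Slopes per year: ln(2.7/4.3)/4.5 = -0.103 and ln(1.3/2.7)/7 = -0.104.
- Ratios at 5.5, 6.5, ..., 12.5 years: 3.32, 2.99, 2.70, 2.43, 2.19, 1.97, 1.78, 1.60.
- The mean is 2.37 for all ages and 2.11 without ages 5-6, a fall of 11%. Without age 5 alone it is 2.24, a fall of 6%.
- With midpoints half a year later (3.5, 8 and 15), the mean goes from 2.50 to 2.23, again a fall of 11%.

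**The case against.** The strongest objection is that the wording is ambiguous rather than wrong, and that its effect is small. Much of this stands.

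- *The rule may be meant for parents.* The usage in Process of Consent allows that. It weakens any claim that children will in fact be excluded, but it does not remove the need to edit: as written, two recruiters could decide the same case differently.
- *The rule does not contradict the age range.* A reader might infer a direct conflict with enrolment from age 5. A 5-year-old who reads satisfies both statements, so this is an unlisted restriction and not a contradiction.
- *Assent is partly oral.* The protocol speaks of age-appropriate communication and of a discussion before signature. The assent form is not among the pages reviewed, so nothing can be concluded about what it provides. Neither statement, however, waives the reading rule.
- *Nothing shows that young children would be removed.* Without reading rates the loss may be nil, so the most that can be said is that they could be under-represented.
- *The highest predicted exposures are not at stake.* A reader might infer that the rule removes the most exposed children. The highest predictions, 5.2 and 4.3, are for ages 1-4, outside the trial. Within it, all of ages 5-10 share the value 2.7, so the documents do not show that 5- and 6-year-olds exceed 7- to 10-year-olds. The interpolated fall of 11%, and a drop in the highest ratio from about 3.3 to 2.7, come from the fitted curve. That curve does not reproduce the protocol's values exactly: it gives 1.60 at age 12 against a stated 1.3, and averages 2.60 over ages 5-10 against 2.7.
- *AUC.* The age ratios are for peak concentration only, so no bias in AUC can be derived from them.
- *Precision.* The documents give no between-child variability. Assuming a coefficient of variation of 30% to 60%, the standard error of a 3-child mean is 0.30/√3 = 17% to 0.60/√3 = 35%, far larger than a shift of 2% to 5%. A bias of that size would hardly be detectable, though averaging does not remove it.

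**Conclusion.** The concern holds in a limited form. The reading rule, taken literally, most naturally applies to the child and is an age-dependent eligibility restriction that the selection criteria do not list. It could under-represent the youngest children in the 5-12 range.

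The loss is 0% to 25% of age-eligible children, and the mean predicted peak silver ratio falls by between 0% and about 2-5% on the stated bands. These figures assume even enrolment by age, and the upper end assumes that no 5- or 6-year-old reads. The spread from 2% to 5% comes from the unstated value for age 11. A fall of about 11% needs the further assumption that the age trend continues within the 5-10 band. The neighbouring bands make that plausible, but the protocol does not state it.

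The direction, towards lower predicted peak exposure, follows from the protocol's own model. The effect on reaching 21 completers is slight given the ceiling of 50. This is a minor point, worth correcting because correction is cheap.

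**What to change.** In Parent/Subject Capacity, require reading and understanding English of the consenting parent only. Require of the child only enough spoken English for age-appropriate assent, and state that the assent form is read aloud to children who cannot read it. List the resulting language criterion in Criteria for Subject Selection, so that all eligibility rules stand in one place, and adjust Documentation of Consent and Assent so that hearing the form read counts as reading it. It would also help to report the age distribution overall and by sampling time, since each child gives a single post-dose sample.

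The cost is a sentence or two in the protocol, a short read-aloud script, and a few extra minutes of staff time for each young child. Sample size and sampling scheme do not change.
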